8.6. Emergency Drug Disclosure

The University of Rochester Medical Center Investigational Drug Service will maintain a list of treatment assignments for each subject and disclose this information upon request in case of a medical emergency. Should drug disclosure occur, the subject in question will be withdrawn from the study.

9. SAFETY AND REPORTABLE EVENTS

9.1. Adverse Event Definition

An adverse event is any symptom, sign, illness, or medical experience that develops or worsens during the course of the study, whether it is attributable to the study drug or not.

9.2. Serious Adverse Event

A serious adverse event is defined as an adverse medical experience that is life-threatening, results in death, requires hospitalization or prolongs an ongoing hospitalization, results in persistent or significant disability or incapacity, and/or requires a medical or surgical intervention to prevent permanent injury or impairment.

9.3. Recording Adverse Events

As specified in the Table, study personnel will screen each subject for adverse events at 7 days, 30 days, 90 days, and 6 months by recording all voluntary complaints of the subject, administering the adverse event questionnaire, and evaluating any available objective clinical findings.

All adverse events, whether observed by study personnel, or elicited from or volunteered by the subject, will be documented. Documentation will include a brief description of the experience, the date of onset, the date of resolution, the duration and type of experience, the severity, any relationship to the study drug, any contributing or alleviating factors, and any action taken with respect to the study drug.

9.4. Responsibilities for Reporting Serious Adverse Events

The Principal Investigator will record all serious adverse events that occur during the study period in an adverse event log. The study period for reporting serious adverse events will be from the time of signing consent until the final study visit at 6 months (*i.e.* 3 months after stopping the study drug). The Principal Investigator will comply with all RSRB policies and regulations regarding the reporting of adverse events.

10. RISK/BENEFIT ASSESSMENT

10.1. Potential Risks and Protection against Risks

Fluoxetine: Potential risks associated with the use of fluoxetine include allergic reaction, anaphylactic shock, depression, suicidal behavior, mania, seizures, serotonin syndrome, neuroleptic malignant syndrome, QT interval prolongation, acute angle-closure glaucoma, abnormal bleeding due to impaired platelet function, hypotension, hyponatremia, and priapism. More commonly, patients report insomnia, headache, anxiety, irritability, dry mouth, tremor, decreased libido, delayed ejaculation, and gastrointestinal symptoms such as nausea, indigestion, constipation, or diarrhea. These side effects typically resolve upon discontinuation of the drug. Subjects will be screened for depression during their enrollment in the study. If, at any point, they are diagnosed with depression, they will be referred to a health care provider for counseling and treatment. If they report suicidal thoughts, they may be directed to the Emergency Department for further evaluation.

Automated Humphrey perimetry, OCT, and neuropsychological testing: The risk associated with these procedures is minimal, the main risk being slight stress, fatigue, or boredom. To minimize these risks, subjects will be encouraged to take breaks, stop the evaluation, or leave the study at any time as they feel necessary. They will also be allowed to bring a family member or companion to the visit. These options will be explained clearly to all subjects prior to enrollment and during the course of the study.

MRI: There are no immediate risks associated with exposure to magnetic fields of 3.0 Tesla. Since the MR gantry is a small opening approximately 3 feet in diameter, the subject may experience anxiety, claustrophobia, or dizziness once he or she is placed inside the MRI machine. In addition, the functional scanning coil closely encloses the subject's head, potentially increasing the likelihood of claustrophobia. To mitigate these risks, the MR gantry is equipped with a camera allowing continuous monitoring of the subject from the control room at all times. In addition, the subject is given a pneumatic bulb that initiates an alarm in the control room when squeezed by the subject in case of an emergency. Furthermore, the subject is able to communicate through an intercom with the operator. Should the subject feel any discomfort, the experiment will be terminated promptly upon his or her request.

Subjects will be screened for magnetic material before each study using an MRI safety screening form (Appendices D1, D2, and D3). Those with pacemakers, implantable cardiac defibrillators, aneurysm clips, penile implants, metallic prostheses including heart valves and cochlear implants, and bullet or shrapnel fragments are at risk of injury in an MR environment. Welders and metal workers are also at risk because of possible metal fragments in their eyes. Those at risk will be excluded from the study.

Scanning by MRI produces a loud tone that can cause injury to the inner ear if appropriate protection is not used. Earplugs or close-fitting silicone-padded headphones will be provided to each subject to prevent ear injury.

The long-term health risks of MRI are unknown. This study will use a magnetic field strength of 3.0 Tesla, which is commonly used in clinical practice and research. This field strength has been used in the clinical setting for nearly a decade, and so far no detrimental long-term effects have been identified.

Phlebotomy: Risks associated with phlebotomy include pain or stinging when the needle is inserted and throbbing and/or bruising at the puncture site after the blood is drawn. To reduce the risk of bruising, subjects will be instructed to hold pressure on the puncture site for several minutes after the needle is withdrawn. Rarely the vein may become inflamed after the blood sample is obtained. This is treated with a warm compress applied several times a day. Finally, there is a small risk of infection at the puncture site. This risk will be minimized by the use of proper sterile technique.

10.2. Potential Benefits to Subjects

Patients randomized to the fluoxetine arm of the study may have improved visual recovery. They also may benefit from the antidepressant effects of fluoxetine. All subjects, whether they are in the fluoxetine or placebo arm, may benefit from depression screening, as depression is common after stroke and associated with poor recovery.

10.3. Alternatives to Participation

Patients may choose not to participate in the study. Unfortunately there are no proven therapies known to enhance post-stroke visual recovery at this time. Standard care for stroke patients with visual field deficits includes occupational and cognitive rehabilitation, which will be offered to all patients regardless of their participation in the study.

11. CONFIDENTIALITY OF DATA AND INFORMATION STORAGE

Subjects' names or initials will not be used when working with the data. Each subject will be assigned a label to maintain confidentiality. While we will make every effort to maintain confidentiality, it cannot be absolutely guaranteed as consent forms and other records that identify study subjects may be inspected by the Department of Health and Human Services and/or authorized officials of the University of Rochester. However, in no case will personal information be shared with other individuals or groups without written prior authorization from the subject. The results of this study may be presented at scientific meetings, published, shared with other researchers, or used in future studies, but data will be maintained in an anonymized form that cannot be connected to any individual subject. Information recorded on paper will be stored inside a locked cabinet in a locked office. All digital data will be password-protected and stored on a firewalled server.

12. RESEARCH INFORMATION IN MEDICAL RECORDS

Most of the data collected during this study will be part of the subject's medical record, including the initial diagnostic MRI, all automated Humphrey perimetry and OCT studies, all ECG studies, and all clinical exam and laboratory findings. The subject's participation in the study will also be documented in the medical record. The results of the neuropsychological assessment, fMRI testing, adverse event questionnaire, PHQ-9 and VFQ-25 questionnaires, and functional vision assessment will not be included in the medical record, but stored in the subject's study binder.

13. DATA ANALYSIS AND MONITORING

13.1. Sample Size Determination

The currently planned enrollment target of 40 subjects (*i.e.* 20 subjects per arm) is intended to achieve a final sample size of 30 and assumes a dropout rate of 25% during the course of the study. In turn, this estimate is based on the number of acute ischemic stroke patients who presented to Strong Memorial Hospital with an isolated visual field deficit in the previous calendar year (56 patients between January 1, 2015 and December 31, 2015). Previous studies indicate that 50% of patients will experience an improvement in their visual field deficit by 3 months. Based on this rate of spontaneous recovery, a final sample size of 15 subjects per group will provide 80% power to detect an improvement rate of 90% in the actively treated group (*i.e.* a 40% difference between the fluoxetine and placebo groups), using a one-sided χ^2 test with $\alpha = 0.05$. Thus, the planned sample size will be sufficient to detect a moderately large effect and is comparable to sample sizes used in equivalent pilot trials evaluating the efficacy of an FDA-approved drug for a novel application.

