1.2. Background

Current strategies in the treatment of ischemic stroke

Despite major advances in acute stroke care over the last two decades, ischemic stroke remains a leading cause of serious long-term disability (1), with 800,000 strokes expected in the United States this year alone. Some form of visual impairment, such as homonymous hemianopia, is present in one to two thirds of all stroke patients (2). Visual impairment, and in particular homonymous hemianopia, is associated with poor prognosis after stroke (3). Complete spontaneous recovery is uncommon (4) although there is some gradual return of visual function due to endogenous repair mechanisms in the first few months (5). At present, there are no proven treatments beyond the first several hours after a stroke that substantially improve functional outcomes. Two decades on, thrombolysis with intravenous (IV) recombinant tissue plasminogen activator (rt-PA) remains the gold standard of acute stroke care in the United States and elsewhere (6). Unfortunately, only 10% of ischemic stroke patients are eligible for this therapy, as the overwhelming majority

of stroke survivors do not present to a hospital within 3 to 4.5 hours of symptom onset. Furthermore, given that not all eligible patients are treated with IV rt-PA (e.g. 77% in 2011) (7), and only 12% of treated patients benefit (6), less than 1% of all ischemic stroke patients may ultimately owe their functional recovery to this time-sensitive treatment. Therapies that enhance recovery beyond the hyperacute stage of the injury have the potential to help a much larger proportion of stroke patients. However, no subacute therapy capable of enhancing post-stroke recovery across the spectrum of stroke etiology, severity, and symptomatology is currently available.

A possible role for SSRIs in improving functional outcomes in stroke survivors

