The visual cortex offers the ideal model system for testing hypotheses about mechanisms of neural plasticity that may be engaged by SSRIs in the post-stroke recovery period. First, in contrast to motor recovery, motivation probably plays a less prominent role in post-stroke visual recovery, as most spontaneous recovery probably occurs early (10) and rehabilitative interventions typically focus on teaching patients compensatory techniques. Second, it is known that fluoxetine can reopen critical periods of neural plasticity in the adult rodent visual system (11). Third, structure-function relationships in the visual system are well understood. The early visual cortex in particular has a highly regular retinotopic organization. Post-stroke changes in this retinotopic map can be characterized and followed by fMRI. Furthermore, cerebral infarction can lead to retinal ganglion cell degeneration through a retrograde trans-neuronal mechanism (12), providing another window through which post-stroke changes in the visual pathway can be monitored and quantified using non-invasive techniques such as optical coherence tomography (OCT). Our research team has demonstrated expertise in characterizing early visual system organization in clinical populations (13). Thus, we are well positioned to assess whether

any observed effects of fluoxetine on post-stroke recovery are due to quantifiable changes in neuronal survival and neural plasticity.

Potential future directions

Fulfillment of this research program has the potential to alter our clinical approach to ischemic strokes affecting the visual system. In addition, answering these questions in the visual system may have more general implications. An understanding of the dynamics and limits of neural plasticity in the post-stroke visual cortex will likely enable us to formulate and test specific hypotheses about how therapeutic interventions like fluoxetine may promote recovery from ischemic strokes affecting other higher-order cognitive functions, including language, praxis, memory, attention, and executive function.

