2.2. Rationale for Study Design

Given the growing evidence that SSRIs may improve motor recovery in stroke survivors, we hypothesize that fluoxetine will also enhance post-stroke functional recovery in the visual system. We further hypothesize that this effect will be mediated through a mechanism independent of the antidepressant and activating effects of fluoxetine. In order to investigate these hypotheses, we have designed a clinical trial in which acute ischemic stroke patients with visual field deficits will be randomized in a 1:1 ratio to fluoxetine *vs.* placebo. The degree of improvement in visual function will then be directly compared between the treatment group and the control group. Because visual recovery after stroke usually plateaus in the first 6 months, we have chosen to treat study subjects for 90 days with fluoxetine *vs.* placebo to determine if exposure to SSRIs during the peak time of recovery improves the rate or degree of recovery. This is also the duration of treatment that was used in the FLAME trial (8).

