13.2. Planned Statistical Analysis

The primary endpoint will be an improvement in peripheral vision of at least 15 degrees in the affected visual field as measured by automated Humphrey perimetry at 6 months. The primary outcome will be compared between the treatment groups using an upper-tailed two-sample *t* test with $\alpha = 0.05$. Secondary outcome measures will include degree of cortical reorganization as assessed by fMRI, RNFL thickness as assessed by OCT, the functional vision score as assessed by the Guide for the Evaluation of Visual Impairment,

performance on neuropsychological testing, and scores on the mRS, PHQ-9, and VFQ-25.

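### The 80% power in section 13.1 is for an improvement of unstated size by 3 months, so it is not established for the primary endpoint of at least 15 degrees at 6 months

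*Combined protocol and SAP*

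**What the plan says.** Section 13.1 (Sample Size Determination) holds the only power statement in the document. Its control rate is: "Previous studies indicate that 50% of patients will experience an improvement in their visual field deficit by 3 months". It gives no size for that improvement, and the sentence carries no reference. It then says that 15 subjects per group "will provide 80% power to detect an improvement rate of 90% in the actively treated group", using a one-sided chi-square test with alpha 0.05, and concludes that "the planned sample size will be sufficient to detect a moderately large effect".

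Section 13.2 (Planned Statistical Analysis) defines the primary endpoint as a gain in peripheral vision "of at least 15 degrees in the affected visual field as measured by automated Humphrey perimetry at 6 months". On the analysis it says: "The primary outcome will be compared between the treatment groups using an upper-tailed two-sample" *t* test, with alpha 0.05.

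Three remarks elsewhere bear on timing. Section 1.2 (Background) says that "most spontaneous recovery probably occurs early" and that "there is some gradual return of visual function due to endogenous repair mechanisms in the first few months". Section 2.2 (Rationale for Study Design) opens its argument for the treatment period with "Because visual recovery after stroke usually plateaus in the first 6 months". Section 3.1 repeats the target of 40 enrolled and 30 at the end, and adds no power inputs.

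**The concern.** The event that was powered and the event that will be tested differ in two ways.

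- **Threshold.** The 50% counts any improvement in the field deficit. The endpoint counts only gains of 15 degrees or more.
- **Time.** The 50% is by 3 months. The endpoint is at 6 months.

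Section 13.1 does not name the 15-degree endpoint. No section gives a control rate, a treated rate, a mean or a standard deviation for it, or argues that the 3-month rate can stand in for it.

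What is at stake is how the result is read. From section 13.1, a reader would take a null result on the primary endpoint as coming from a trial with 80% power for a moderately large effect. The document does not support that reading. Section 1.1 also lists the feasibility of larger trials as an objective, and those planning such trials would need to know what effect on this endpoint 15 per arm can detect.

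**Working it through.** **Inputs from the document.** 40 enrolled and 25% dropout give 40 × 0.75 = 30, or 15 per arm at 1:1 (sections 13.1 and 8.3). Control rate 50%, treated rate 90%, one-sided alpha 0.05 (z = 1.645), chi-square test (section 13.1).

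**Formula.** Normal approximation with pooled variance under the null, where d = p2 − p1 and p̄ = (p1 + p2)/2:

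power = Φ{ [d − 1.645 × √(2p̄(1−p̄)/n)] / √([p1(1−p1) + p2(1−p2)]/n) }

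**The plan's own figure.** p̄ = 0.70.
- Null standard error: √(2 × 0.70 × 0.30/15) = 0.1673, and 1.645 × 0.1673 = 0.2752.
- Alternative standard error: √((0.25 + 0.09)/15) = 0.1506.
- Power: Φ[(0.40 − 0.2752)/0.1506] = Φ(0.829) = 0.796.

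The stated 80% is therefore sound for its own inputs.

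**Moving to the primary endpoint.** The document gives no rates for a gain of at least 15 degrees at 6 months, so no single figure can be computed. The two gaps may also pull in opposite directions: a size threshold would tend to bring the control rate below 50%, and a later assessment would tend to raise it.

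To show how much this matters, the effect in 50% vs 90% can be carried to other control rates in three ways: a difference of 40 points, a risk ratio of 0.90/0.50 = 1.8, or an odds ratio of (0.9/0.1)/(0.5/0.5) = 9. Every control rate other than 50% is an assumption, and none is preferred.

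Example at an assumed control rate of 30%:
- Difference: 30% + 40 points = 70%, power Φ[(0.40 − 0.3003)/0.1673] = 0.724.
- Ratio: 30% × 1.8 = 54%, power Φ[(0.24 − 0.2964)/0.1748] = 0.373.
- Odds ratio: odds 0.3/0.7 × 9 = 3.857, so 79.4%, power Φ[(0.494 − 0.299)/0.158] = 0.892.

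Treated rate, then power, at 15 per arm and one-sided 0.05:

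| Control rate | 40-point difference | Risk ratio 1.8 | Odds ratio 9 |
|---|---|---|---|
| 5% (assumed) | 45%: 0.841 | 9%: 0.111 | 32.1%: 0.612 |
| 10% (assumed) | 50%: 0.796 | 18%: 0.154 | 50%: 0.796 |
| 20% (assumed) | 60%: 0.741 | 36%: 0.248 | 69.2%: 0.890 |
| 30% (assumed) | 70%: 0.724 | 54%: 0.373 | 79.4%: 0.892 |
| 40% (assumed) | 80%: 0.741 | 72%: 0.551 | 85.7%: 0.859 |
| 50% (section 13.1) | 90%: 0.796 | 90%: 0.796 | 90%: 0.796 |
| 60% (assumed) | reaches 100% | exceeds 100% | 93.1%: 0.705 |

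For control rates of 10% to 40%, power is 0.72 to 0.80, 0.15 to 0.55 and 0.80 to 0.89 on the three scales.

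**The test.** Section 13.1 powers a chi-square test and section 13.2 plans a *t* test. Applied to a 0-1 response at 50% vs 90%, a one-sided *t* test has power 0.793 by enumeration, against 0.796 above. If the *t* test is meant for degrees gained as a continuous measure, a mean difference and a standard deviation would be needed, and the document gives neither.

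**The case against.** The strongest reply is that the link is merely unstated. Sections 13.1 and 13.2 are adjacent, both speak of improvement, and both use a one-sided 0.05 level. The sponsor may have meant 50% and 90% as response rates for the 15-degree endpoint. That is possible, but the text does not say so. If it was meant, a sentence with a justification closes the point.

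On timing, the two Background remarks give real support to a 3-month rate as a rough stand-in for 6 months, although section 2.2 places the plateau only somewhere within the first 6 months. The time gap is therefore partly answered. Nothing comparable answers the 15-degree threshold. The Background does cite natural-history and recovery papers, but whether any of them supports the 50%, or a rate for 15 degrees, cannot be judged from the document.

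It is also fair to say that enrolment was tied to feasibility (56 such admissions in 2015) and to comparable pilot trials. That explains the sample size, and it is why no change to it is asked for. It does not support the separate claims of 80% power and of sufficiency.

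A reader might infer that a stricter threshold must cost power. It need not: if it lowers the control rate to between 10% and 40% at a constant odds ratio, power is at or above the plan's own 0.796. A reader might also make much of the conflict between chi-square and *t* test. On a binary response it moves power by only 0.003, so it adds little weight here.

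**Conclusion.** The point holds as a mismatch between the power statement and the primary endpoint. The 80%, and the sentence on sufficiency, are established only for 50% vs 90% with an improvement of unstated size by 3 months. For the primary endpoint, power is undetermined and the direction of any error is unknown.

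It would be tempting to conclude that the trial is underpowered, or that section 13.1 contains an arithmetic error. The document supports neither: the calculation reproduces, and plausible scenarios lie on both sides of 80%.

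The width of the range rests on assumed control rates and on which effect scale is held constant, and the document fixes neither. The threshold gap carries most of the weight. This should be fixed, but it changes neither the sample size nor the conduct of the trial.

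**What to change.** Keep enrolment at 40 and revise section 13.1 in one of two ways.

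1. State and justify, with a source, the control and treated rates for a gain of at least 15 degrees at 6 months. If the 3-month improvement rate is used as a proxy, justify it for the threshold as well as for the time point.
2. If that cannot be done, say that the 80% applies only to 50% vs 90% for improvement by 3 months, and limit the sentence on sufficiency in the same way. Then give power for the primary endpoint at 15 per arm over a labelled range of assumed rates, on the difference, ratio and odds-ratio scales.

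In either case, name one test suited to the binary endpoint in both 13.1 and 13.2, and compute the power for that test.

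The cost is some text, a citation or justification, and at most one small table. Visits, endpoint and sample size stay as they are. The downside is that the protocol may no longer be able to quote a single 80% for its primary endpoint.
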